### Hypothesis:

The addition of acoustic stimulation linked to brain activity (HIRREM plus continued current care, HCC) will be associated with greater reduction in the frequency and severity of hot flashes experienced than that seen with continued current clinical care alone (CCC), among patients with perimenopausal and postmenopausal vasomotor symptoms.

### Research Design and Method:

#### Objectives:

##### Primary Objective:

The primary objective of this pilot study is to evaluate whether the addition of acoustic stimulation linked to brain activity (HIRREM, HCC) to continued current clinical care, will reduce the frequency and severity of vasomotor symptoms, as compared with continued current clinical care (CCC) alone in patients with documented perimenopausal and postmenopausal vasomotor symptoms.

##### Secondary Objectives:

Evaluate whether the addition of HCC to continued current clinical care will result in greater differential changes in a variety of physiological, behavioral, and function outcome measures outlined below, as compared to CCC.

[figure not shown]
1. Autonomic nervous system functions, as manifested by heart rate, HRV, and BRS. We expect to see greater changes in autonomic activity and an improvement of sympatho-vagal balance in the HCC group. This would be reflected as changes in heart rate, and an increase of HRV and BRS parameters such as the standard deviation of the R-R interval (SDRR), rMSSD, HF alpha, and Sequence Up, Down, or All.
2. Reduction in menopause-related scales: Menopause Rating Scale (MRS) and Hot Flash Related Daily Interference Scale (HFRDIS). We anticipate to see greater improvement in these symptoms in the HCC group.
3. Behavioral outcomes such as insomnia (assessed by the Insomnia Severity Index, ISI; Pittsburgh Sleep Quality Index, PSQI; and the Epworth Sleepiness Score, ESS), depression (as assessed by the Center for Epidemiological Studies-Depression Scale, CES-D), anxiety (as evaluated by the GAD-7), and stress (as assessed by the Perceived Stress Scale, PSS). We expect to see greater improvement in these symptom inventory scores in the HCC group.
4. Overall quality of life as evaluated using the QOLS. We hope to see greater improvement in overall quality of life scores in the HCC group.
5. Functional performance evaluated using drop stick reaction testing. We expect to see more improvement in the HCC group.
6. Functional performance evaluated by grip strength, using a hand dynamometer. We expect to see greater improvement of grip strength in the HCC group.

### Overview:

[figure not shown]
This will be a randomized, single site, pilot clinical trial. Assuming a potential drop-out rate of 20%, up to 48 subjects will be enrolled to achieve a goal of having at least 40 subjects (20 per group) complete the study, per protocol. Patients who have at least 5 hot flashes per day (with at least one being categorized as moderate to severe) will be eligible to participate.

Those who have no other exclusions, are interested to participate, and provide informed consent will be randomly assigned to receive 8-16 sessions of in-office acoustic stimulation linked to brainwave activity (HCC), over a maximum of 4 weeks, while continuing their other current clinical care, or to continue their current clinical care alone (CCC). There will be pre- and post-intervention data collection to include a daily hot flash diary (to be completed for 7-14 days by both groups) and many secondary outcome measures including completion of the MRS, HFRDIS, measures of autonomic cardiovascular regulation (continuous recording of BP and HR for calculation of measure of HRV and BRS), behavioral symptom outcomes (ISI, PSQI, ESS, CES-D, GAD-7, PSS), quality of life measure (QOLS), and function performance measures (drop stick reaction testing, and grip strength). All measures will be collected at an enrollment visit (V1). Both groups will then maintain a hot flash diary for 7-14 days, after which the intervention will begin for the HCC group. Post-intervention data collections will include an intermediate post-intervention visit (V2, primary outcome, 4-6 weeks after intervention completion for HCC, and 10-12 weeks after V1 for CCC), and a final follow up visit (V3, 12-14 weeks following completion of the intervention for HCC, and 18-20 weeks after V1 for CCC). Both groups will maintain a hot flash diary for 1-2 weeks prior to the V2 and V3 visits. The primary outcome will be reduction in frequency and severity of hot flashes score from V1 to V2. Following V3, those in the CCC group will be offered the opportunity to receive a course of HCC within 3 months (will have another brainwave assessment 0-14 days before beginning sessions), and will continue to be followed for data collections at 4-6 weeks (V4), and 12-14 weeks (V5) after completing their HIRREM sessions.

## Hot Flash Study Flow Chart

## CCC Group Who Complete V1-V3 and Choose to Receive a Course of HCC

### Participants/Subjects:

Women ages 40 and older with self-reported perimenopausal and postmenopausal related vasomotor symptoms, who meet the following inclusion criteria and are interested to participate in the study will be recruited from the community by physician referral and advertisement. Each subject must be able to provide an informed consent. The criteria for inclusion will be those experiencing at least five hot flashes per day (with at least one being categorized as moderate to severe).

Interested subjects will be informed with a more detailed description of the study, and the extent of their commitment, through phone calls or email communications. If no exclusions are apparent from initial phone or email communications, potential participants will complete an online eligibility screening form, which will be reviewed by the study team. If potential participants express continued interest in the project and have no major exclusions, they will be scheduled for an enrollment visit (V1) at which time an informed consent will be completed. Those scheduled for an enrollment visit will also be provided a copy of Appendix B, Handout to Study Participants, and/or a welcome email with details.

As part of the informed consent process, study procedures, schedule for visits, and duration of participation will again be reviewed, and alternatives discussed, including the option to not enroll in this project, and follow up with their primary health care provider.

After informed consent is obtained, randomization will be completed, baseline study measures obtained, and all participants will be instructed how to maintain a hot flash daily diary.

### Inclusion Criteria:

Women, age 40 or older, with perimenopausal and postmenopausal related vasomotor symptoms (intact uterus and ovaries), who have at least 5 hot flashes per day (with at least one being categorized as moderate to severe), with what is reported to be a stable pattern for at least one month.

### Exclusion Criteria:

Less than 5 hot flashes per day

Does not experience at least 1 moderate to severe hot flash per day

Unable, unwilling, or incompetent to provide informed consent

Physically unable to come to the study visits, or to sit comfortably in a chair for up to two hours

Known seizure disorder

Known or potential pregnancy (females with last menstrual period less than one year from enrollment will be tested for pregnancy prior to randomization)

Severe hearing impairment (because the subject will be using headphones during the interventions)

Ongoing need for treatment with opiate, benzodiazepine, or anti-psychotic medications, anti-depressant medications such as SSRI, SNRI, or tricyclic, and sleep medications such as zolpidem or eszopiclone

Use of pharmaceuticals for treatment of vasomotor symptoms or any type of hormone replacement therapy

Use of supplements for improvement of vasomotor symptoms including but not limited to black cohosh, soy isoflavone extract, and red clover leaf extract  
Menopausal symptoms resulting from, or associated with surgery, chemotherapy, radiation, or use of other chemicals or medications  
Anticipated and ongoing use of recreational drugs, alcohol, or energy drinks  
Ongoing need for treatment with thyroid medications  
Weight is over the chair limit (285 pounds)  
Are enrolled in another research study that includes an active intervention  
Have previously received brainwave optimization (BWO), used a B2 or a B2v2 wearable device, or previously participated in a HIRREM research study

Participants are encouraged to discuss their participation with their health care provider following completion of the study because HIRREM may alleviate some of the need for medications they were on previously. Participants are requested to abstain from using any alcohol or recreational drugs during the intervention, and for at least six weeks following sessions since use of these substances may cause reversal or cessation of the benefits of HIRREM. In addition, the participants are also advised to suspend chiropractic, cranial-sacral therapy, and bio-energy work during the intervention, and for at least six weeks following.

#### Number of Subjects:

As a pilot study, in a new cohort of participants, using a wait-list control, we are not able to calculate an accurate sample size. In order to evaluate feasibility and effect size, and allowing for up to 20% drop outs, we will arbitrarily enroll up to 48 subjects to achieve a goal of having 40 subjects complete the study per protocol (estimated 20 per group).

#### Number of HCC Sessions and Length of Study:

All baseline measures, along with a brainwave assessment, will be obtained during an enrollment visit (V1). The intervention will commence 7-14 days later. Participants will receive 8 to 16 in-office intervention sessions over a maximum of 4 weeks. HCC sessions will be about 1.5-2 hours in length. All will receive a total of 6 sessions during the first three days of the intervention period. Following the initial 6 sessions, some sessions may be arranged as singles (one per day), if needed due to schedule issues. Participants will be encouraged to complete the remainder of the intervention sessions within two-three weeks, with a maximum of four weeks to complete the sessions. If done as two sessions per half day, subject involvement will thus require 4-8 half days during the intervention period.

At the primary post-intervention data collection visit, all measures will be repeated. This visit will occur at 4-6 weeks after completion of the intervention for the HCC group, and 10-12 weeks after V1 for the CCC group. A final data collection visit (V3) will occur 12-14 weeks after completion of the intervention for the HCC group, and 18-20 weeks after V1 for the CCC group, with repeat of the outcome measures, but no brainwave assessment. At V3, official study involvement is complete for those in the HCC group, while those randomized to the CCC group will be offered an opportunity to be scheduled to receive a

course of HCC within 3 months. Participants who cross over will have a brainwave assessment 0-14 days before starting sessions. Those who opt to do so will receive a course of in-office acoustic stimulation linked to brainwaves, as described for the HCC group, and will continue to be followed for data collections at 4-6 weeks (V4), and 12-14 weeks (V5), as done during the initial intervention period, after completing their HCC sessions.

#### Enrollment Visit:

Informed consent is obtained, notification of group assignment is made, and all baseline measures are collected, including a brainwave assessment. The V1 visit will require about 2 hours of time.

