Methods: This will be a randomized, single site, pilot clinical trial, enrolling up to 40 women, who have at least 5 hot flashes per day (with at least one being categorized as moderate to severe), and who are not taking medications or supplements for management of hot flashes. Participants will be randomly assigned to receive 8-16 sessions over a maximum of 4 weeks of acoustic stimulation linked to brain activity (HIRREM and continued current care, HCC) or will be assigned to a waitlist group (continued current care, CCC). Both groups will continue their other current care throughout. There will be pre- and post-intervention data collection to include physiological outcomes (BP, HR, and measures of autonomic cardiovascular regulation), as well as daily hot flash diaries, Hot Flash Related Daily Interference Scale (HFRDIS), the Menopause Rating Scale (MRS), symptom inventories for insomnia (Insomnia Severity Index, ISI; Pittsburgh Sleep Quality Index, PSQI; and the Epworth Sleepiness Score, ESS), depression (Center for Epidemiological Studies- Depression Scale, CES-D), anxiety (Generalized Anxiety Disorder-7, GAD-7), stress (Perceived Stress Scale, PSS), and a quality of life measure (Quality of Life Scale, QOLS), as well as drop stick reaction testing, and dynamometry for grip strength. Measures will be collected at an enrollment visit (V1). Both groups will then maintain a hot flash diary for 7-14 days, after which the intervention will begin for the HCC group. Post-intervention data collections will be obtained at 4-6 weeks (V2, primary outcome) and 12-14 weeks (V3) following completion of the intervention. Follow up data collection for the CCC group will occur at 10-12 weeks (V2), and 18-20 weeks (V3) after the V1 visit. Both groups will maintain a hot flash diary for 1-2 weeks prior to the V2 and V3 visits. The primary outcome will be differential change in hot flash frequency and severity from

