V1 to V2 between HCC and CCC, based on data from the hot flash daily diary. Following V3, those in the CCC group will be offered the opportunity to cross over to receive a course of HCC within 3 months, and will continue to be followed for data collections at 4-6 weeks (V4), and 12-14 weeks (V5) after completing their crossover HIRREM sessions. Additional mean contrasts will be constructed to evaluate the consistency of any benefit of HIRREM through subsequent visits beyond V3. Comparisons of changes in all secondary outcomes will be assessed in a similar fashion.

Importance: This study will explore the use of HIRREM for vasomotor symptoms associated with menopause in a randomized, clinical trial. The study will confirm feasibility using a closed-loop, acoustic stimulation intervention for a randomized clinical trial in this population, and will also provide estimates of effect size, which might justify larger controlled trials. A positive result would suggest that HIRREM might have benefit as a noninvasive, non-drug alternative for management of vasomotor symptoms. This, over and above the potential benefit from participating in a clinical trial, and interacting with the study personnel and the study environment. The study will also help to identify the characteristics of subgroups that might experience differential effects/benefits from HIRREM.

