#### Menopause -related symptoms:

Hot flash diaries provide a valid and reliable approach to understanding a participant's experience of hot flashes and night sweats (Sloan et al., 2001). An adapted hot flash daily diary that includes daytime and nighttime frequency and severity will be included. Categories are mild (1), moderate (2), severe (3), and very severe (4). Data will be used to calculate a hot flash severity score for each day as the sum number of hot flashes within each severity category multiplied by the severity score of that category, with the resulting sum divided by the total number of hot flashes. Participants will be asked to keep a 7-14 day daily hot flash diary after V1, and then 7-14 days before each subsequent data collection visit.

Hot Flash Related Daily Interference Scale (HFRDIS) is a 10 item measure to capture the daily impact of vasomotor symptoms in a variety of domains within the past week. These domains include work, social activities, leisure activities, sleep, mood, concentration, relation with others, sexuality, enjoyment of life, and overall quality of life. Items are scored from 1 (not at all) to 10 (extremely) (Carpenter, 2001).

The Menopause Rating Scale (MRS) is a survey that generates a score between 0 and 44 based on the individual's symptom severity rankings (Research, 2008). There are 11 symptoms listed related to perimenopause that are each assigned a score of 0 to 4 by the individual. A score of 0 indicates none, 1 is mild, 2 is moderate, 3 is severe, and 4 is very severe. After completion, the individual's score is tallied to create an overall score. Scores from 0-4 are considered zero to little, scores from 5-8 are considered mild, scores from 9-16 are moderate, and scores 17 or greater are considered severe.

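### Women learn their group at V1, and the entire 7-14 day baseline diary for the primary outcome is kept after that

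*Combined protocol and SAP*

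**What the plan says.** The Enrollment Visit section describes V1 in one sentence: "Informed consent is obtained, notification of group assignment is made, and all baseline measures are collected, including a brainwave assessment". The Participants/Subjects section also places randomization at that visit: "After informed consent is obtained, randomization will be completed, baseline study measures obtained, and all participants will be instructed". The instruction mentioned there concerns the diary.

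The diary itself comes later. The section on menopause-related symptoms says "Participants will be asked to keep a 7-14 day daily hot flash diary after V1", and the Overview, after describing V1, says "Both groups will then maintain a hot flash diary for 7-14 days, after which the intervention will begin for the HCC group". The Methods paragraph of the Abstract agrees. No diary before V1 is described. Eligibility on hot flash count rests on self-report and an online screening form.

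The Abstract takes the primary outcome, a between-group comparison of change in how often and how badly flashes occur, from this diary: "V1 to V2 between HCC and CCC, based on data from the hot flash daily diary". The control is a wait-list. The Overview says "Following V3, those in the CCC group will be offered the opportunity to receive a course of HCC within 3 months", and V3 for that group is 18-20 weeks after V1.

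**The concern.** Hot flash count and severity are rated by the woman herself. While she fills in the baseline diary, a woman in the HCC group knows that her sessions start within 14 days. A woman in the CCC group knows that hers are offered only after V3. If that knowledge changes how the two groups report, the baseline differs between groups for a reason unrelated to their symptoms, and the difference enters the V1-to-V2 contrast. Adjusting for baseline does not remove it, because the covariate is itself recorded after disclosure. No diary kept before randomization exists against which a shift could be checked.

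The contrast will be used. The Abstract says the pilot "will also provide estimates of effect size, which might justify larger controlled trials".

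**Working it through.** The plan gives no figure to reproduce here. The check is first one of sequence, then of what a shift would do.

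**Sequence**
- Day 0 (V1): consent, randomization, notification of group, visit-based measures, diary instruction.
- After V1, for 7-14 days: baseline diary, both groups.
- Day 7-14: first session, HCC only.

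Diary days after disclosure: 7 of 7 up to 14 of 14, that is 100%. The order of steps within V1 does not matter. Two sections say that all baseline measures are obtained at V1, but a 7-14 day diary cannot be completed in a visit of about 2 hours, and three places in the text put it afterwards.

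**Effect of a shift.** Let d be the differential reporting shift at baseline (HCC minus CCC, flashes/day), p the share of it that persists at V2, and b the baseline slope if the analysis adjusts for baseline. None of these is in the documents; d = 1, p = 0 to 1 and b = 0.5-0.7 are assumed.
- Now, unadjusted change: pd - d = d(p - 1).
- Now, baseline-adjusted: d(p - b).
- Diary completed before randomization, either analysis: the baseline term is 0 and the V2 term is dp.

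| p | Now, unadjusted | Now, b = 0.5 | Now, b = 0.7 | After the change |
|---|---|---|---|---|
| 0 | -1.0 | -0.5 | -0.7 | 0 |
| 0.5 | -0.5 | 0 | -0.2 | +0.5 |
| 1 | 0 | +0.5 | +0.3 | +1.0 |

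For d > 0 a negative entry looks like a benefit of HIRREM; for d < 0 all signs reverse. The total is smaller after the change if p < 1 - p, so p < 0.5 (unadjusted), or if p < b - p, so p < b/2 = 0.25 to 0.35 (adjusted).

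**Illustration of the extreme case.** Take 20 completers per group (Number of Subjects), no true effect, a two-sided 5% t test with 38 degrees of freedom, an unadjusted change and p = 0. A shift of s SDs of the change gives a noncentrality of s × sqrt(20/2). For s = 0.1, 0.2, 0.3 and 0.5 (assumed), the rejection probability is 6.1%, 9.5%, 15.2% and 33.8%. At p = 0.5 each shift counts half, so s = 0.2 gives 6.1%.

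**Room in the schedule.** The first session may fall at most 14 days after V1. If diary return, randomization and booking take 1, 3, 5 or 7 days, the longest diary is 13, 11, 9 or 7 days, so the 7-day minimum still fits. With 3 days (assumed):
- Earliest start: 7 + 3 = day 10, against day 7 now.
- Latest HCC V2: 14 + 28 + 42 = 84 days = 12.0 weeks. Latest V3: 14 + 28 + 98 = 140 days = 20.0 weeks. Neither moves.
- Earliest HCC V2 (8 sessions, two per day, over 4 days): 7 + 3 + 28 = 38 days = 5.4 weeks now, and 10 + 3 + 28 = 41 days = 5.9 weeks after.
- SD of the diary mean, 11 days against 14: sqrt[(r + (1 - r)/11) / (r + (1 - r)/14)] = 1.002, 1.009 and 1.019 for an assumed between-day correlation r of 0.8, 0.5 and 0.3.

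**Extra consents.** For 48 randomized with 5-20% non-return (assumed): 48/0.95 = 50.5, rounded up to 51, and 48/0.80 = 60. That is 3-12 extra V1 visits.

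**The case against.** The strongest objection is that the change is not shown to lower bias. Women know their group through V2 in either design, and nothing in the documents says that less than half of a shift would fade or persist. If it persists in full, the present order cancels it in an unadjusted contrast and the new order leaves all of it; if it grows (p > 1), the new order is again worse. This stands. It limits what may be claimed for the fix, but it does not make a baseline recorded after disclosure sound: the present order helps only if a shift among women awaiting sessions is still there, close to unchanged, 4-6 weeks after those sessions end.

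The diary also precedes every session and covers the same window in both groups, so treatment does not contaminate it. That is true; the exposure is knowledge of group, not treatment.

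The costs are also wider than a remote return. The Intervention Period section requires the first six sessions on three consecutive days, and the Exclusion Criteria require pregnancy testing before randomization for some women. Both interact with a later randomization. This stands and is taken up in the fix.

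Four stronger readings are tempting and not supported:
- That reporting is in fact biased, or that the false-positive rate is inflated by a known amount. The rates above rest on an assumed shift, in the case where none of it persists and no adjustment is made.
- That the plan fixes an unadjusted diary contrast. The Statistical Analysis section writes its model only for blood pressure, V1 to V3, and allows model adjustments; no diary model is given.
- That the V1 questionnaires are certainly answered after notification. Participants/Subjects lists randomization before the baseline measures, but the Enrollment Visit sentence is a list and does not fix the order.
- That moving randomization would remove reporting bias. It would remain at V2 and V3.

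**Conclusion.** The point holds in a limited form. Confidence is high that all 7-14 baseline diary days follow disclosure of group, and that nothing elsewhere in the plan repairs this. The amount and direction of any bias are unknown: 0 to 1.0 flash/day per 1 flash/day of differential shift in an unadjusted contrast, for persistence from 1 to 0.

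Completing the diary before randomization does not guarantee less total bias. What it gives for any size of shift and any persistence is a primary baseline that cannot depend on group and is valid as a covariate, with reporting bias confined to follow-up, where it can be named. This should be fixed as a cheap improvement; it is not a fatal flaw. Stating a limitation alone would cost nothing, but it leaves an avoidable exposure in the primary outcome.

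**What to change.** **Changes**
- Participants/Subjects and Enrollment Visit: at V1, obtain consent, the visit-based baseline measures and the brainwave assessment, and give the diary instruction. Randomize and notify by phone or email only after the completed baseline diary has been returned remotely, and before the first session.
- Abstract (Methods), Overview and the section on menopause-related symptoms: state that the baseline diary is completed before randomization. Give its maximum length in line with the turnaround (11 days if 3 are allowed). Leave the V2 and V3 diaries at their present length and analyze all diaries as means per day.
- Reconcile the new order with three places: the start 7-14 days after V1 (Number of HCC Sessions and Length of Study), whose earliest days may no longer be attainable; the six sessions on three consecutive days (Intervention Period), for example by holding provisional slots for all women at V1; and pregnancy testing before randomization (Exclusion Criteria), which would no longer fall at the same visit as randomization if testing stays at V1.
- Number of Subjects: say whether the cap counts randomized women, reconcile 48 here with 40 in the Abstract, and report the number consented but not randomized.
- State unmasked reporting at V2 as a limitation.

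**Cost**
- No visit is added for any randomized woman, but a remote return must be set up.
- HCC women get less notice for booking. With an 11-day diary, 3 days cover return, randomization, notification and booking together. A start missed for this reason would fall after randomization and in HCC only.
- A maximum diary of 11 days instead of 14 raises the SD of its mean by 0.2-1.9% under the assumed correlations.
- The brainwave assessment is 10-14 days old at the first session instead of 7-14, still within the 0-14 days set for crossover.
- Women who do not return the diary are not randomized. This is a compliance run-in: it selects the sample and moves some drop-out to before randomization, so it should be reported as a feasibility result.
- At an assumed 5-20% non-return, 3-12 extra V1 visits of about 2 hours are needed, and 3 × $25 = $75 to 12 × $25 = $300 if the per-visit payment applies.
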